This study (Figures 1 and 3) will include Option A consisting of 9 lab visits each approximately 2 hours long, except visit 1, which will last up to 3 hours **OR** Option B consisting of 5 lab visits each containing 2 vaping sessions separated by a 3-hour washout period and lasting approximately 6 hours. Figure 2 illustrates the study e-cig and e-liquid variations. Figure 3 depicts the sequence of the proposed study. We will conduct an experimental study examining how the manipulation of nicotine form (nicotine salt (NSB) vs. free-base (FB)) influences vaping behavior, abuse liability, toxicant exposure and heart and lung health.

Evaluating E-Cigarette Nicotine Form, Concentration, and Flavors among Youth

Figure 1. Vaping Session

Vaping Session	
12 hour nicotine abstinence	
Start of Session:	Surveys Respiratory Measures Cardiovascular Measures Blood Draw (0 min)
STD Puffing (5 min):	Blood Draw (5 min) Surveys
Ad-lib Puffing (30 min): Blood Draw (10 min) Blood Draw (35 min) Surveys	
3-hour washout (Visits 2-5 between vape sessions) (Option B Only)	
3 hrs. post exposure:	Respiratory Measures Cardiovascular Measures (Option B Only)
1 vaping session will occur at each visit for 9 visits (Option A Only)	
1 vaping session will occur at the first visit / 2 vaping sessions will occur at the final 4 visits (Option B Only)	

Figure 2. E-cig and e-liquid for Vaping Sessions

[figure not shown]
[figure not shown]

Figure 3. Study Sequence Option A and Option B

Evaluating E-Cigarette Nicotine Form, Concentration, and Flavors among Youth

ii. Study Procedures

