
1. Recruitment Feasibility and Retention

a) Recruitment

We intend to recruit 130 e-cig users from the community over an 18-month period and have them complete nine study visits (Option A) or five study visits (Option B); therefore, we need 3-4 participants to be recruited and complete study procedures per month.

We are confident our recruitment approach, laboratory facilities, and equipment redundancy will result in a sufficient participant processing rate, given our successful completion of other tobacco-related research of similar design⁴¹. E-cig users will be recruited from advertisements through a variety of media outlets and the internet, including Study Search, as well as community events. Participants from

Evaluating E-Cigarette Nicotine Form, Concentration, and Flavors among Youth

other studies who have agreed to be contacted regarding other study opportunities will also be contacted. Staff from those studies will prepare contact letters/emails and call participants on behalf of this study. Interested participants will be referred to this study for screening. Participants will access the screening questionnaire using a public survey link generated by REDCap. Based on our team's previous studies, we conservatively assume a 20% attrition rate. Thus, we need to recruit 130 participants to have 60 complete the study. Participants who meet the following eligibility criteria will be asked to take part in the study.

Inclusion criteria: 1) a current e-cigarette user (≥ 1 vaping bout per day) for at least the past 3 months , 2) 21-25 years old, 3) willing to abstain from all tobacco and nicotine for at least 12 hours prior to lab sessions, 4) willing to complete nine lab visits/vaping session lasting up to 2 hours each or five lab visits lasting up to 6 hours each (except Visit 1) , 5) able to read and speak English, 6) willing to provide informed consent

Exclusion criteria: 1) self-reported diagnosis of lung disease including asthma, cystic fibrosis, or chronic obstructive pulmonary disease, 2) history of cardiac event or distress within the past 3 months, 3) currently pregnant (determined using urine pregnancy test), planning to become pregnant, or breastfeeding, 4) use of other tobacco products >10 days in the past month, 5) current marijuana use >10 times per month, 6) currently engaging in a vaping cessation attempt.

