Participants' eligibility will be determined over the phone or via REDCap's online screener. Those who are eligible and willing to participate will be invited to sign an informed consent and complete their baseline visit in a private participant room at the Ohio State University. All participants will be given adequate time to review the informed consent with a trained research staff to help answer any questions that may arise during the consent process. Additionally, a copy of the informed consent will be given to all participants. A pregnancy test will be completed at the initial visit as well as before starting all the in-lab visits to ensure that the participant is not pregnant.

b) Retention and Compensation

If participants choose Option A, they will receive \$50, \$50, \$50, \$50, \$75, \$75, \$75, \$75, and \$100 for completing visit 1, 2, 3, 4, 5, 6, 7, 8, and 9, respectively, for a total of \$600. Participants who choose Option B will receive \$50, \$100, \$125, \$150, and \$175 for completing visit 1, 2, 3, 4 and 5, respectively, for a total of \$600. Consistent with our previous studies, payments will be made using the Greenphire ClinCard to increase accountability and facilitate ease of payment. We will facilitate visits by offering weekend appointments and using additional retention strategies (e.g., reminder calls/texts/emails). Participants will receive reminder calls in addition to email or text reminders. Reminders will be sent by text or email based on a participant's preferred method of contact.

2. Detailed Study Procedures

a) Study Sessions

Prior to the start of the first laboratory visit, twelve-hour tobacco abstinence will be assessed via self-report and confirmed with exhaled carbon monoxide testing ($eCO \leq 10$ ppm). A research assistant will

Evaluating E-Cigarette Nicotine Form, Concentration, and Flavors among Youth

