Inclusion of Women and Minorities: According to U.S. Census Data, 51.3% of Columbus, OH residents are female. In our previous studies with smokers, 55-62% of participants were female. According to U.S. Census data, the racial composition of individuals living in Columbus is 61% White, 28% Black or African American, 5% Asian, 0.2% American Indian/Alaska Native, 0% Native Hawaiian/Other Pacific Islander, and 4% two or more races. The ethnic composition of individuals living in Columbus is 6% Hispanic/Latino. We expect that our distributions will be similar to these but we may potentially have a larger distribution of ethnic and racial minorities, based on our previous studies. However, we will continuously monitor enrollment in order to ensure that we are meeting recruitment goals to avoid under-recruiting minorities. If the targeted enrollment for minorities is not met because they do not

Evaluating E-Cigarette Nicotine Form, Concentration, and Flavors among Youth

respond to the advertisements, we will make special efforts to solicit their participation by advertising in community newspapers, local church organizations, and community centers.

ii. Inclusion of Children

This study will be restricted to individuals 21 years of age and older, which is the legal age to purchase tobacco products.

G. Human Participants

i. Recruitment and Informed Consent

At first contact, all participants will be screened according to the study's inclusion/exclusion criteria. Those who are eligible will be given a brief verbal overview of the study and invited to participate. Informed consent (including a description of the nature, purpose, risks, and benefits of the study) of the participant will take place through both oral and written explanation of the study. The voluntary nature of the study and the participant's right to withdraw at any time will be stressed during the consent process. A copy of the informed consent will be provided to the participant in written form at the time of consent for them to keep. Informed consent will be collected by IRB approved study personnel. Recruitment script and materials, consent forms, and all study procedures will be approved by the OSU Institutional Review Board. All participants will provide written consent before any study data is collected.

ii. Potential Risks and Protections against Risk

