Nevertheless, all participants will be screened for general medical precautions (pregnancy, cardiovascular disease) and monitored for adverse events during the study period. Study personnel will assess for adverse events via self-report at all follow-up visits. Any serious adverse events will be reported to the study's DSMB, and then to the OSU IRB and to the NIH. We will withdraw participants who have a serious adverse event, or become pregnant, begin to breastfeed, or have a cardiovascular or pulmonary event during the study. The most likely adverse (potential for nicotine overdose) event is anticipated to be rare (<5% in our team's previous studies) and mild (nausea, headache, disrupted sleep), and will be handled quickly (i.e., advice to participant to reduce or stop e-cig use). Lab studies of toxin exposure suggest that e-cigs incur no greater risk to health than do conventional cigarettes. Indeed, e-cigarettes generally show lower levels of harmful and potentially harmful constituents. To date, e-cigarette studies discussing adverse events report mild and tolerable side effects that generally resolved completely over time with continued use; the most predominant of which were mouth/throat irritation, cough, and headache. In four randomized clinical trials, no serious adverse events were reported, and the e-cigarette group and the nicotine patch group had comparable levels of adverse events in two studies. The most common were mouth irritation, throat irritation, dry cough and headache. Following the completion of the study, we will encourage all participants to quit their use of e-cigarettes.

2. Loss of Confidentiality and Privacy:

Risks

There is a risk of breach of confidentiality or a loss of privacy associated with taking part in the study.

Protections

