The data and safety monitoring plan will involve the continuous evaluation of safety, data quality and data timeliness. Investigators will conduct continuous review of data and patient safety at their regular Disease Group meetings (at least monthly). The PI of the trial will review toxicities and responses of the trial where applicable at these disease center meetings and determine if the risk/benefit ratio of the trial changes. Frequency and severity of adverse events will be reviewed by the PI and compared to what is known about the agent/device from other sources; including published literature, scientific meetings and discussions with the sponsors, to determine if the trial should be terminated before completion. Serious adverse events and responses will also be reviewed by the OSUCCC Data and Safety Monitoring Committee (DSMC). The PI will also submit a progress report (biannually for Phase II and quarterly for Phase I) that will be reviewed by the committee per the IRB of record as per the policies of the IRB. All Serious Adverse Events are to be submitted to the DSMC for their review. Submissions are made via OnCore.

Adverse Events

Adverse events will be assessed by study staff at each visit via participant self-report and managed immediately. All adverse events will be reported to the OSU IRB. We will monitor for risk of smoking/vaping by screening participants for general medical precautions (pregnancy, cardiovascular disease). Any adverse events, breaks of confidentiality, or any other data or safety issues that arise will be discussed immediately between study personnel and [name]. [name] will be responsible for completing an Adverse Events Form should an event occur. [name] will report Serious Adverse

Evaluating E-Cigarette Nicotine Form, Concentration, and Flavors among Youth

Events to the OSU IRB within 24 hours of having received notice of the event. [name] will gather any information needed to investigate the event and to determine subsequent action. Any subsequent action will be documented and reported to the OSU IRB and the Program Officer at NIH. Adverse event reports will be reviewed annually with the OSU IRB to ensure participant safety.

Collection of Adverse Events

The collection of adverse events will be on a self-report basis and logged within an electronic data capture system (REDCap) or collected using standardized paper forms and will only be identified with the study ID of the participant.

I. Addendum

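### Screening for cardiovascular disease is named as a protection, but no listed exclusion makes a cardiovascular diagnosis disqualifying

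*Combined protocol and SAP*

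**What the plan says.** Section G.ii.1 (Risk of Using ECs, Protections) says that "all participants will be screened for general medical precautions (pregnancy, cardiovascular disease". The Adverse Events part of Section H repeats this, saying that vaping risk will be monitored by "screening participants for general medical precautions (pregnancy, cardiovascular disease". Section G.i says that at first contact "all participants will be screened according to the study's inclusion/exclusion criteria".

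Section D.ii.1.a lists six inclusion and six exclusion criteria. Exclusion 2 is the only one about the heart: "history of cardiac event or distress within the past 3 months". Exclusion 1, for the lung, is worded by diagnosis: "self-reported diagnosis of lung disease including asthma, cystic fibrosis, or chronic obstructive pulmonary disease". Pregnancy is exclusion 3, and the same section adds that "A pregnancy test will be completed at the initial visit as well as before starting all the in-lab visits".

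Once a person is enrolled, Figure 1 puts these items at the start of each session, before any puffing: "Surveys Respiratory Measures Cardiovascular Measures Blood Draw (0 min". Section G.ii.1 withdraws participants who "have a cardiovascular or pulmonary event during the study".

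**The concern.** A stated protection should correspond to a rule that acts on what the screening finds. Here the risk section names a disease, while the eligibility list names only an event or an episode of distress. A site applying the list as written has no listed ground for turning away someone who reports a cardiovascular diagnosis but no such event or distress.

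The exposure matters because the plan itself expects acute effects. Section A hypothesizes greater adverse cardiovascular effects with salt and menthol liquids, and the Abstract cites arterial stiffness and altered hemodynamics and platelet activity in e-cigarette users. Half the test liquids are at 5% nicotine. A pod is also taken home for practice between visits 1 and 2, out of sight of staff, and it may be a 5% liquid.

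**Working it through.** The plan gives no figure to reproduce, so the check is a comparison of the texts.

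1. **What is promised.** Two conditions are named as general medical precautions, in both Section G.ii.1 and Section H: pregnancy and cardiovascular disease.

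2. **What the criteria deliver for each.**
   - Pregnancy: a listed exclusion, with a urine test at the initial visit and before in-lab visits.
   - Cardiovascular disease: 0 of 6 inclusion criteria and 0 of 6 exclusion criteria name a cardiovascular diagnosis. One of the 6 exclusions is cardiac, and it covers an event or distress.
   - Lung disease, for comparison: excluded by self-reported diagnosis, with no time window.

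3. **The time limit in exclusion 2.** Most naturally, the 3 months applies to both the event and the distress, so an older event does not exclude. It could grammatically apply to distress alone. Either way, a diagnosis with neither an event nor distress is not on the list. Distress is undefined and may catch some symptomatic disease, but it is not a diagnosis.

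4. **Whether another entry step closes the gap.** Eligibility is settled by phone or the REDCap screener (Section D.ii.1.a). The on-site checks in Section D.ii.2.a are exhaled carbon monoxide and the pregnancy test. Blood pressure and heart rate are measured (Section D.ii.2.a, Table 1), but no value is given that bars or stops exposure. The withdrawal rule acts only after an event during the study.

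5. **Exposure that follows from entry.** The design has 2 forms × 2 concentrations × 2 flavors = 8 liquids, of which 2 × 1 × 2 = 4 are at 5%. Someone who completes all sessions therefore has 4 × 10 = 40 directed puffs and up to 4 × 30 = 120 minutes of ad libitum use at 5%. This is every completer's planned exposure. It shows what an admitted person would receive, and does not measure how often the gap would matter.

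**The case against.** The strongest reply is that Sections G.ii.1 and H make a screening commitment in their own right. Section G.i ties first-contact screening to the criteria but does not say that no other screening takes place, and the phone/REDCap screener is not in the documents. It may well ask about cardiovascular disease and turn people away. This stands as a limit on the point. A reader might infer that a diagnosed person is eligible however the plan is read, and the documents do not support that. They show that the listed criteria do not exclude such a person, and that nothing in the text says what happens if screening finds the disease.

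A second reply is that the risk section is simply shorthand for exclusion 2. That is possible. The gap would then be loose wording in the risk section, but the listed criteria would still admit a diagnosed person.

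A third reply concerns the comparison with the lung criterion. Spirometry, exhaled nitric oxide and airway reactivity are outcomes, so excluding asthma and similar disease may serve measurement as well as safety. This also stands: the difference in wording does not by itself prove an oversight.

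Finally, there are real safeguards. Participants are 21-25 and have vaped at least daily for 3 months. Visit 1 uses their own product and includes blood pressure and heart rate before a study device goes home. Adverse events are asked about at each visit, and the smoking rooms can be observed from outside. Section B.2 notes that 5% was the strength the market leader first sold. These lower the concern without removing it: no cut-off is attached to the readings, and inclusion 1 sets no nicotine strength, so 5% may exceed a person's usual product.

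**Conclusion.** The point holds in a limited form. The plan says it screens for cardiovascular disease, yet its listed criteria do not make a cardiovascular diagnosis disqualifying. A diagnosed person without a recent event or distress would be eligible for 5% exposure unless the screener applies the Section G.ii.1 commitment separately. It is a safety point worth considering, not a serious defect, and it rests on the criteria as printed.

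No magnitude can be stated, because the documents give no prevalence. A reader might try to supply one. If 0.1% to 2% of the 130 recruits were affected (an assumption), the chance of at least one such person would run from 1 − 0.999^130 = 12% to 1 − 0.98^130 = 93%. For the 60 completers, who alone receive the full exposure, it would run from 1 − 0.999^60 = 6% to 1 − 0.98^60 = 70%. Both ranges are too wide to say anything, and they assume that neither exclusion 2 nor the screener catches anyone. They should not be cited as the size of the problem.

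A reader might also infer that the contrasts between liquids are biased. That is not claimed: each participant is their own control for form, concentration and flavor.

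**What to change.** Extend exclusion 2 so that a self-reported diagnosis of cardiovascular disease also excludes, placed ahead of the existing text "history of cardiac event or distress within the past 3 months", and confirm that the phone/REDCap screener has the matching item. State briefly what counts as cardiovascular disease, for example whether mild hypertension does, so that screeners apply it consistently.

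Keep the investigators' window for events and distress. A lifetime bar on any past cardiac event is tempting, but it goes beyond the discrepancy and would replace their choice with a preference. Rewording Sections G.ii.1 and H to match exclusion 2 would restore consistency but protect nobody, so it is the weaker option.

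The cost is a minor protocol amendment, one screener item if it is not already there, and probably very few extra exclusions at ages 21-25. Sample size and analysis do not change.

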explain the study to the participant and answer any questions they may have. The participant will give an exhaled breath sample into the handheld CO monitor to determine if they are eligible to participate in the laboratory vaping session. If the participant's exhaled CO concentration ≤ 10 ppm, they are deemed eligible to participate further, and will be asked to read the informed consent form. Once all participant questions have been answered, the participant will be asked to sign their consent to participate in the study. Pregnancy exclusion will also be confirmed with a urine test. Participants will be asked to avoid eating (anything), drinking coffee, tea, sodas, juice, alcohol, and smoking (including any cigarette/nicotine replacements such as electronic cigarettes) at least 3 hours prior to their visit since that will affect the results of certain measures. Participants will not be allowed to eat or drink (other than water) during the vaping sessions, but will be provided a light snack prior to IV placement and the start of vaping sessions. Participants will be allowed to eat and drink during the 3-hour washout periods for Option B visits 2-5.

First, participants will complete background measures (Sociodemographic Measures, Tobacco Use History (including the Timeline Followback (TLFB) interview– week, month, lifetime and the Sensory E-Cigarette Expectancies Scale (SEES)⁴²), and the E-Cig Dependence (modified Cigarette Dependence Scale)⁴³. To measure nicotine uptake, a forearm venous catheter (placed by the research nurse) will be used to sample blood (~ 5 mL) as participants complete an initial 30-minute ad libitum vaping session using their own e-cig device and e-liquid. Blood will be collected at 4 time points (t=0, 5, 10, and 35 minutes) during each vaping session.

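### Option B allows eating and drinking with no stated limit in the 3-hour washout just before heart and lung measures, although the plan restricts intake for 3 hours before visits because it affects results

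*Combined protocol and SAP*

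**What the plan says.** All the intake rules stand in one paragraph of Study Sessions (D.ii.2.a).

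- Before a visit: "Participants will be asked to avoid eating (anything), drinking coffee, tea, sodas, juice, alcohol, and smoking". The period and the reason follow: "at least 3 hours prior to their visit since that will affect the results of certain measures". The measures concerned are not named.
- During vaping: "Participants will not be allowed to eat or drink (other than water) during the vaping sessions".
- Before vaping, in both options, participants "will be provided a light snack prior to IV placement and the start of vaping sessions". The order of this snack relative to the baseline heart and lung measures is not given.
- In the Option B washout: "Participants will be allowed to eat and drink during the 3-hour washout periods for Option B visits 2-5". No limit is stated on type, amount or timing.

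Figure 1 (D.i) shows the washout as "3-hour washout (Visits 2-5 between vape sessions) (Option B Only"). Its next row, at 3 hours post exposure, reads "Respiratory Measures Cardiovascular Measures (Option B Only"). Each session also opens with respiratory and cardiovascular measures.

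The design text in D.ii justifies the washout only by the return of nicotine to baseline. Table 1 lists no measure of food or drink. Section E gives gender as its only example of a covariate, and E.ii adds a fixed effect for session and a random effect for sequence.

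**The concern.** The plan gives its own reason for restricting intake, then lifts the restriction for an interval of the same length just before heart and lung measures are taken. In Option B, coffee or a meal during the washout can therefore affect two things: the 3-hour value that follows the first liquid of the visit, and the baseline for the second liquid. Nothing in the listed data would show afterwards who had consumed what.

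At stake are the cardiovascular and pulmonary parts of H1b. Section E names spirometry and flow-mediated dilation among the outcomes. The 3-hour row of Figure 1 is marked Option B only, and the figure lists no other heart and lung measures after vaping. The problem therefore touches all the post-vaping values of this kind that the figure shows.

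**Working it through.** **Timeline of an Option B visit (visits 2-5), in minutes from the first puff.** Inputs: 5 minutes of standardised puffing, 30 minutes ad libitum and a 3-hour washout (Figure 1 and D.ii).

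- End of session 1: 5 + 30 = 35.
- End of washout: 35 + 180 = 215. The 3-hour measures for session 1 and the starting measures for session 2 fall here.
- End of session 2: 215 + 35 = 250, or 4.2 hours.

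The pre-visit restriction is at least 180 minutes and the washout is 180 minutes. Anything consumed in the washout therefore lies within the interval that the plan says affects results.

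A further 180 minutes after session 2 would end at 430 minutes (7.2 hours), against a stated visit length of about 6 hours. Whether session 2 has a 3-hour measure is therefore unclear.

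**Number of intake episodes.** Four visits with one washout each give four episodes per Option B participant. Each episode bears on two analytic roles: the post value for the first liquid and the baseline for the second. The documents do not say whether these are one physical set of measurements or two. If one set serves both roles, a shift from intake moves the two change scores of that visit in opposite directions.

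**Which comparisons are affected.**

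- Change from baseline to 3 hours: the pre-visit restriction governs the baseline but not the 3-hour value, so intake can bias the change.
- Second-session against first-session baseline: the same asymmetry applies. The session effect can absorb an average shift, but not the part that varies by person and visit.
- Liquid against liquid, within person, in Latin Square order: intake unrelated to the liquid adds variance but no bias. Intake that depends on the liquid just vaped would add bias.

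**Size of the noise.** The plan's own figure (E.i) is 80% power for main effects at alpha 0.01 and an effect of 0.5 SD of the paired differences. With N=60 from D.ii, a two-sided paired t-test (sidedness is not stated) has noncentrality 0.5 × √60 = 3.87 and a critical value of 2.66 on 59 degrees of freedom. Power is 88.2%, so the stated 80% is met; 51 participants would be enough.

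The documents give no figure for the effect of intake. As an assumption, let it add a fraction q to the variance of the paired difference. The effect in SD units becomes 0.5/√(1+q).

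| q (assumed) | Effect (SD) | Noncentrality | Power at N=60 |
|---|---|---|---|
| 0 | 0.500 | 3.87 | 88.2% |
| 0.10 | 0.477 | 3.69 | 84.4% |
| 0.25 | 0.447 | 3.46 | 78.5% |

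The table treats every participant as choosing Option B. The documents do not give the share who will; a smaller share means a smaller loss.

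**The case against.** The strongest reply is that H1a to H1c compare liquids, and that the order of liquids is randomised within each participant. A shift common to all liquids cancels in the paired difference, and the session effect takes up an average difference between first and second sessions. This stands.

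A reader might infer that the Option B heart and lung results are confounded as a whole, or that a shift from intake could use up much of the 0.5 SD effect for which the trial is sized. The documents do not support either reading. The 0.5 SD in E.i is a difference between conditions, not a change from baseline, so the two cannot be set against each other. No section names the change from baseline as the estimand, and nothing in the documents shows that intake differs by liquid.

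Four further replies have some force:

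- The plan asks participants to avoid intake; it does not describe an enforced ban. It does not name the affected measures either. That they include heart and lung measures is a reasonable inference, not stated text.
- The snack before IV placement may precede the baseline measures in both options, so the baseline may not be fasted either. This weakens a simple contrast of a fasted baseline with an unfasted 3-hour value, but it is a further reason to fix the order.
- Quality Assurance (D.ii.3) promises operating procedures and a checklist for each visit with the order of measures. These could settle where the snack falls. They would not by themselves remove the written permission to eat and drink in the washout.
- Food was presumably allowed because the visit lasts about 6 hours and follows a fast. The fix should therefore keep food available.

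**Conclusion.** The point holds in a limited form. The intake rules in Study Sessions do not fit the measurement times in Figure 1. Four washouts per Option B participant carry uncontrolled and unrecorded intake into the 3-hour heart and lung values of the first session and the starting values of the second.

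Bias is possible in the change from baseline to 3 hours and in the comparison of second-session with first-session baselines. For the randomised comparisons between liquids, the expected harm is loss of precision. Under the assumed 10% to 25% extra variance, main-effect power stays near the planned 80%, at 84% or 79%. That range is an illustration, not an estimate. Bias between liquids would need intake to depend on the liquid just vaped, which cannot be checked unless intake is recorded.

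The change is worth making because the rule works against the plan's own stated reason and is cheap to correct.

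**What to change.** Reconcile the intake paragraph in D.ii.2.a with Figure 1:

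- Apply the plan's own pre-visit drink list to the Option B washout, with water allowed.
- Keep food in the washout the same in content and timing at every visit, and give it only after the post-vaping surveys. Food given straight after the 35-minute draw would precede the liking, craving and withdrawal scales in Option B only.
- State that the snack before IV placement follows the baseline respiratory and cardiovascular measures, in both options.
- Record the time and type of any intake, and name it in Section E as a covariate or for a sensitivity analysis.
- State whether the end-of-washout measures are one set or two, and whether session 2 has a 3-hour measure.

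The cost is protocol wording, one checklist line and less freedom to eat and drink during a visit of about 6 hours. No extra visits or tests are needed.
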